3.2 Aims and Objectives

In this study, we propose to study in a 1:1 randomized controlled trial the diagnostic accuracy of navigation bronchoscopy (NB) with F-Nav (SuperDimension iLogic 7.2 ENB platform and later (SuperDimension, Medtronic, Minneapolis, Minnesota, USA)) using a non-inferiority study design (primary endpoint) versus the current clinical standard of care: CT-guided biopsy. We will in addition compare: complications rate including rate of pneumothorax and clinically significant bleeding, need for hospitalization

CONFIDENTIAL

after procedure, time to procedure, duration of the procedure, need for additional nodule biopsy, need for additional procedure for staging, radiation exposure from fluoroscopy and CT, and need for F-Nav during navigation bronchoscopy (secondary endpoints). Follow up has been chosen to be pragmatically deliverable while allowing full assessment of key outcomes, including false negatives to provide a robust, clinically meaningful trial result.

4. Study Design

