4.1 General Study Design

This is a randomized 1:1 non-inferiority trial of the new diagnostic algorithm versus the current standard of care. A non-inferiority design has been chosen to reflect the clinically most important outcome (diagnostic accuracy) in the presence of a technology which is likely to reduce significant current complications / adverse events, and allow in the same procedure mediastinal staging and, potentially, additional bronchoscopic interventions (such as airway inspection, biopsy of additional nodules).

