4.6 Intervention Arm: Bronchoscopy Pathway

The intervention arm will consist of electromagnetic (EMN) navigation bronchoscopy using the Medtronic SuperDimension platform with F-Nav. Patients' available DICOM CT images will be uploaded into the planning software. CTs obtained more than 21 days before the planned procedure, and CT not meeting minimal technical requirements for optimal roadmap planning (adequate CT reconstructions and slice thickness of 1.5mm or less) will be repeated before the procedure. Bronchoscopy will be performed by interventional pulmonologists with expertise in navigation bronchoscopy (as defined by more than 100 procedures performed in the past 2 years, with at least 25 of these performed with F-Nav). Procedures will be performed under general anesthesia with neuromuscular blockade (to facilitate breath holds required for FNAV image acquisition) in a dedicated bronchoscopy suite or operating room. Bronchoscopy will be performed as previously described with confirmation by radial ultrasound.¹⁷ Suggested intraprocedural flow is detailed in the figure in section #14. Radial ultrasound will be used for confirmation only, and not as a navigational tool (i.e. catheters not aligned with the registered target will be considered non-diagnostic). Biopsies will be obtained using a any-gauge needle, with at least 5 passes obtained per nodule. Forceps biopsies, brushings or other biopsy tools will be performed according to the procedure algorithm. Rapid on-site evaluation will be performed to assess for specimen adequacy. All procedures will be followed by fluoroscopy evaluation of the chest to exclude pneumothorax, and, if indicated, ultrasound and/or formal chest radiograph as per standard of care. The procedure will be deemed non-diagnostic if the proceduralist is unable to reach the nodule or if a complication occurs and therefore no biopsy is obtained.

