4.7 Comparison: CT-guided Biopsy Pathway

The control arm of the study will consist of CT-guided biopsy, which will be performed by interventional radiologists with expertise in transthoracic needle biopsy and/or fine needle aspiration (as defined by more than 25 procedures performed in the past two years as a department). Procedures will be performed in a dedicated interventional CT scanner with multi-slice capabilities. Patient analgesia with local anesthesia and moderate conscious sedation will be used. Biopsy number, core biopsy vs. fine needle aspiration, use of coaxial needles, and use of rapid on-site cytologic examination will be at the discretion of the proceduralist per local institutional preferences. Procedures will be followed by limited CT scan and/or chest radiograph to exclude pneumothorax if required per local standard of care. The procedure will be deemed non-diagnostic if the proceduralist is unable to reach the nodule or if a complication occurs and therefore no biopsy is obtained.

- 1. Patients not eligible for general deep sedation and general anesthesia and therefore not eligible for bronchoscopy, but potentially eligible for CT-guided biopsy, will be excluded from the study but recorded as such in the CONSORT diagram.**
- 2. Patients randomized who fail to present for their assigned intervention will be considered screen-failure**
- 3. Patients randomized who present for their assigned intervention but do not undergo the procedure for reasons other than for contraindications to the procedure (per institutional policy) will be analyzed as non-diagnostic procedure, and otherwise considered screen-failure. The cause for cancellation will be recorded in the case report form.**

CONFIDENTIAL

See Procedural Flow Chart (Section 14).

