4.8 Outcomes

Primary endpoint

The primary endpoint will be diagnostic accuracy, as defined by the rate of technically successful biopsies leading to a definitive diagnosis, comparing the navigation bronchoscopy to the CT-guided biopsy pathway. Definitive diagnoses are pre-defined as any of the following:

- Malignancy on histological samples, **OR**
- Biopsies with abnormal tissue (excluding normal or absence of lung parenchyma) that are followed by a surgical lung biopsy yielding the same histological diagnosis, **OR**
- Specific benign histopathologic finding which accounts for the presence of a lung nodule (specifically including organizing pneumonia, frank purulence, granulomatous inflammation, or other specific benign finding) **AND**
- Absence of malignancy (true negative) over 1 year of longitudinal CT follow-up, defined as:
 - the nodule markedly regresses or resolves on follow-up imaging, **OR**
 - a persistent nodule has not been diagnosed as malignant, **AND**
 - there are no plans for repeat invasive diagnostic procedures through 12 months follow-up.

Biopsies with normal or absence of lung parenchyma, atypia or mild inflammation will be considered non-diagnostic. All diagnoses (from both arms) will be determined by a blinded, independent, expert lung pathologist (i.e. blind to the biopsy technique) and all non-diagnostic biopsy specimens will be reviewed by an independent expert pathologist.

Linear EBUS for lymph node interrogation and staging will be performed in the same procedure after the navigation bronchoscopy for staging purposes as per standard of care.

Secondary endpoints

- Rate of pneumothorax
- Rate of pneumothorax requiring chest tube placement
- Clinically significant bleeding (defined by bleeding requiring intervention)
- Need for hospitalization after procedure
- Duration of the procedure (from bronchoscope in to bronchoscope out for the bronchoscopy arm and from first needle in to last needle out for CT-guided biopsy)
- Procedural factors associated with improved yield (type of biopsy, number of biopsies, use of radial ultrasound, presence of a bronchus sign, biopsy site)
- Need for additional nodule biopsy
- Need for additional procedure for staging

CONFIDENTIAL

- Radiation exposure from fluoroscopy-guided bronchoscopy and CT for CT-guided biopsy
- Need for F-Nav during navigation bronchoscopy
- Adequacy of specimens collected for molecular testing when needed.

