6.3 Variables Recorded

- Past medical history
- Demographic data
- Smoking history
- Occupational history
- Current medications
- Laboratory data (complete blood count, electrolytes, creatinine, coagulation profile if available, results of fungal serologies if available)
- Chest CT characteristics:
 - Location of the nodule (lobe and segment)
 - Nodule size (longest axis)
 - Distance to the nearest visible bronchus on either CT plane (axial, coronal or sagittal)
 - Bronchus sign (airway aligned with nodule)
 - Distance to the nearest parietal pleura
- PET scan characteristics (FDG uptake (SUV))
- Procedural characteristics:
 - Duration of procedure
 - Number and type of biopsies
 - Use of FluoroNav, and divergence in mm if used
 - Radiation exposure
 - Complications (pneumothorax, bleeding, others)
- Time to procedure (delay between decision to biopsy and procedure)
- Time from identification of nodule to treatment for malignant nodules
- Need for another biopsy modality
- Need for an additional staging procedure
- Follow-up data.

7. Safety Reporting of Adverse Events

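### Procedure duration is timed over different spans in the two arms, so part of any between-arm difference will come from the definitions

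*Combined protocol and SAP*

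**What the plan says.** Section 4.8 lists procedure duration as a secondary endpoint and times it "from bronchoscope in to bronchoscope out for the bronchoscopy arm and from first needle in to last needle out for CT-guided biopsy". The synopsis lists the same endpoint without a definition.

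Section 3.2 makes it a between-arm comparison. The outcomes to be compared include "time to procedure, duration of the procedure, need for additional nodule biopsy, need for additional procedure for staging".

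Section 4.8 also says, in a separate paragraph: "Linear EBUS for lymph node interrogation and staging will be performed in the same procedure after the navigation bronchoscopy for staging purposes". Section 4.1 gives as one reason for the design that NB can "allow in the same procedure mediastinal staging and, potentially, additional bronchoscopic interventions".

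Section 6.3 records one item on this subject, "Duration of procedure". It lists no separate time for nodule sampling, for EBUS or for the whole session.

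**The concern.** A comparison of durations means something only if the two clocks start and stop at equivalent points. Here one clock covers the time the bronchoscope is in the patient, and the other covers needle time only. If NB is recorded as longer, a reader cannot tell whether reaching and sampling the nodule took longer or whether more of the work was timed.

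Staging makes this harder to interpret. The protocol presents same-session staging as an advantage of NB, and the need for an additional staging procedure is a secondary endpoint of its own. If EBUS falls inside the NB clock, the duration endpoint charges NB for that advantage, while the time CT patients later spend on staging is not counted in their duration. The recorded gap would then also depend on how often EBUS is done. If sites disagree on whether EBUS counts, it would depend on site practice too.

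**Working it through.** The plan states no mean, standard deviation, effect size or power for duration, so there is no figure to reproduce. The check sets the sections side by side.

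**Before sampling.**
- NB (Section 4.6): the clock starts at scope insertion. It therefore runs through navigation, F-Nav image acquisition and ultrasound confirmation ("Bronchoscopy will be performed as previously described with confirmation by radial ultrasound").
- CT (Sections 4.7 and 4.8): the clock starts at the first needle. Any imaging used to localise the nodule before that is not counted. CT imaging between the first and last needle is counted.
- Result: guidance before sampling is counted for NB and not for CT.

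**After sampling.**
- NB: EBUS is placed in the same procedure, and nothing stops the clock before it. The natural reading is that scope out comes after EBUS. However, EBUS is also described as coming after the navigation bronchoscopy, so a site could stop timing when navigation ends.
- CT: the clock stops at the last needle. A later staging procedure appears only under its own endpoint.
- Result: the plan does not say whether staging time is counted for NB, and it is never counted for CT.

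**Steps that do not separate the arms.**
- Post-biopsy check: in the CT arm, "Procedures will be followed by limited CT scan and/or chest radiograph to exclude pneumothorax if required per local standard of care". Section 4.6 likewise places the NB fluoroscopy check after the procedure. It may lie outside both clocks.
- On-site evaluation: planned for NB in Section 4.6 and allowed at the proceduralist's discretion for CT in Section 4.7. It may fall inside both clocks.
- NB planning from CT images, and anesthetic induction before the scope goes in, are outside the NB clock. This works in the opposite direction.

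**Does any section reconcile the clocks?** None was found in Sections 3.2, 4.1, 4.6 to 4.8, 6.2 or 6.3. The flow chart in Section 14 was not available in the text reviewed.

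**How large an offset would matter (illustration only).** Take 112 per arm from Section 6.1. Assume that the true like-for-like difference is zero, that the definitions alone add a constant offset d, and that the SD is the same in both arms. The values of d and SD are assumed, because the documents give none. For a two-sided 5% test:

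- SE = SD × √(2/112)
- Chance of a nominally significant result ≈ Φ(d/SE − 1.96)
- Example: d = 10 min, SD = 20 min. SE = 20 × 0.1336 = 2.67, and 10/2.67 − 1.96 = 1.78, which gives 96%.

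| Assumed SD | d = 5 min | d = 10 min | d = 20 min |
|---|---|---|---|
| 10 min | 96% | >99% | >99% |
| 20 min | 46% | 96% | >99% |
| 30 min | 24% | 70% | >99% |

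Over this range, an offset of a few minutes to 20 minutes could be enough to produce a nominal difference. The table does not show that the offset in this trial is of that size.

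**The case against.** The best defence is that both definitions follow one recognisable rule, instrument in to instrument out, stated in advance and open to any reader. Duration is one of many secondary endpoints, and Section 6.2 attaches no test or decision rule to it. The likely distortion lengthens NB time, so it does not flatter the investigational arm. The staging trade-off is visible in a separate endpoint. Each of these is correct and keeps the point minor. None makes the two spans equivalent: an instrument-based rule can describe each arm, but it does not support the comparison promised in Section 3.2.

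A reader might infer more than the documents support:

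- **That EBUS is certainly inside the NB clock.** This is the natural reading, but no section states it. Section 3.1 links staging to confirmed malignancy and Section 4.8 to standard of care, so EBUS may apply only to some patients.
- **That on-site evaluation and the post-biopsy check widen the mismatch.** Neither is shown to differ between the clocks.
- **That the whole observed difference would be an artefact.** A real difference in working time may also contribute.
- **That the built-in gap can be put at some number of minutes.** Any such figure needs assumed EBUS and CT set-up times, and would also have to consider the NB planning and induction left out.

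**Conclusion.** The duration comparison is not like for like as defined. This holds whether or not EBUS is inside the NB clock, because guidance before sampling is counted in one arm and not in the other. Relative to a clock running from first guidance to last sample, the definitions tend to lengthen recorded NB time, and more so where EBUS is counted.

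Part of any observed difference would therefore come from the definitions. How much cannot be derived from the documents. The conclusion rests on the wording of Sections 3.2, 4.6, 4.7 and 4.8, and on the assumption that the Section 14 flow chart does not define the timing differently. The primary endpoint, its margin and the sample size are not affected. It is a minor point, worth correcting because the correction is cheap.

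**What to change.** In Sections 4.8 and 6.3:

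1. Start both clocks at the first guidance step: scope in for NB, first localising scan for CT.
2. End both clocks when the last nodule-sampling tool is out.
3. State that EBUS time is excluded from the compared duration, and record EBUS start and stop separately.
4. Report total session time in both arms as a second line, for example from room or sedation start to end. This also captures NB induction. Say that it includes EBUS where EBUS was done.
5. For attempts in which no sampling tool was used, the matched clock has no end point. Give their number by arm and report their total session time.

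The cost is a few extra timestamps on the case report form. The change concerns measurement only and alters no care. For patients already treated, recover times from procedure records where possible and report how many are missing by arm. Where matched times cannot be recovered, report the durations as now defined descriptively by arm, with each definition beside them and no between-arm test.

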4.9 Centralized Pathology Review (Core Lab Confirmation)

An independent expert lung pathologist will review all non-diagnostic and benign cases. In case of disagreement with the initial pathology review, a third expert lung pathologist will adjudicate the case.

In all cases, management after intervention-biopsy will be as per standard of care, i.e. patients will be managed according to a participating site's conventional clinical guidelines. For example, patients after a negative biopsy may (1) cross-over to another minimally invasive biopsy, (2) be followed with serial chest CTs or (3) undergo surgery. These subsequent procedures will be part of normal patient care and only be regarded as follow-up data for the purpose of this study (i.e. non-randomized bronchoscopies and CT-guided biopsies will not affect the diagnostic yield for the purpose of this study).

Patients will be followed for up to 12 months if serial imaging by chest CT if clinically indicated (non-malignant pathology without resolution on interval imaging), with suggested scanning cadence at 3 months, 6 months, and 12 months.

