The diagnostic algorithm for indeterminate pulmonary nodules is based on pre-test probability of malignancy as determined by validated clinical prediction scores or clinician estimates. Low-probability (<10% chance of malignancy) are followed radiologically with serial CT, while high pre-test probability nodules (>70% chance of malignancy) are typically surgically resected, although tissue confirmation is often necessary even for these nodules.⁵ A non-surgical biopsy is typically recommended for nodules with low to intermediate probability of malignancy. High pre-test probability nodules are also frequently biopsied, when surgery is considered higher-risk or when stereotactic body radiation therapy is considered. Options include CT-guided transthoracic needle biopsy or bronchoscopic biopsy. CT-guided biopsy is associated with a general yield estimated at 90%, although studies focusing on nodules < 1.5 cm have reported yields between 70% and 80%.⁶⁻⁸ There has not been randomized controlled studies comparing CT-guided biopsy to other approaches. The technique is associated with substantial complications: in a population-based study, the rate of pneumothorax was 15% with need for chest tube management in 7%, and the risk of hemorrhage was 1%.⁹ Conversely, bronchoscopic biopsy is safer with reported 1.6% pneumothorax, with a need for chest tube management in 0.7%, and a 0.5% hemorrhage risks, but best estimates of yield using conventional navigation techniques approach 75%, with rates below 50% in registry data.¹⁰⁻¹²

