One of the main limitations of navigation bronchoscopy is the inability to confirm successful navigation, as the roadmap planning to the nodule is based on preoperative CT images obtained at lung volumes substantially different than those achieved during deep sedation or general anesthesia required during bronchoscopy. The recently introduced FDA-approved enhanced fluoroscopy imaging device, F-Nav (SuperDimension, Medtronic, Minneapolis, Minnesota, USA), allows visualization of fluoroscopically-invisible nodules, re-registration and adjustment of the target. Using this more “real time” technique, the diagnostic yield approaches 85% in retrospective data from Vanderbilt University Medical center, Nashville, TN. In addition, endobronchial ultrasound biopsies of mediastinal lymph nodes are diagnostic in 13% of patient without CT or PET scan abnormalities, which emphasizes the importance of bronchoscopy.¹³ If these promising results were confirmed, the widespread adoption of F-Nav would allow diagnostic resolution of indeterminate pulmonary nodules with the following advantages over CT-guided biopsy: (1) avoidance of potentially life-threatening complications associated with CT-guided biopsies, (2) performance of complete mediastinal staging via endobronchial ultrasound when malignancy is confirmed, in a single procedure under a single sedation / anesthetic session and (3) potential biopsy of multiple indeterminate lung nodules in the same procedure. This has the potential to significantly decrease mortality, morbidity and healthcare costs, and if proven, to be a robust diagnostic methodology, to become the standard of care for thousands of patients per year.

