6.1 Statistical methodology

This study will be a randomized controlled trial of navigation bronchoscopy vs. CT-guided biopsy using a non-inferiority study design. The hypothesis of the study is that the diagnostic accuracy of EMN navigation bronchoscopy using the SuperDimension platform with F-Nav performed by interventional pulmonologists is non-inferior to the diagnostic accuracy of CT-guided biopsy performed by interventional radiologists. Eligible patients will be randomized on a 1:1 basis and the randomization will be stratified by the following two criteria within each center to provide balance between treatment arms on these features:

1. Location in the middle or outer third of the lung
2. Pre-test probability of malignancy (50% or less VS 51% or more)

Within each stratum, block sizes of 2 and 4 will be used to enhance blinding.

Though the primary analysis will use a Bayesian approach, the initial power analysis uses a Frequentist approach. We assume that a diagnostic accuracy for CT-guided biopsy is 90%. The non-inferiority margin is set at 10 percentage points, and one-sided type I error rate is set at 5%. Thus, if the true diagnostic accuracy for navigation bronchoscopy is lower than 80%, we will have 5% probability (type I error rate) to incorrectly conclude noninferiority. With this parameter setting a sample size of 112 per group will give approximately 80% power if the true diagnostic accuracies are 90% for both arms. Considering an attrition rate of 15%, the sample size is 129 per group (258 total). Large volume centers could be expected to enroll 50 patients per year, therefore 6 centers are necessary. One year recruitment plus one year follow-up represents 2 years of recruitment time. The noninferiority margin has been chosen based on the known pneumothorax rate of CT

CONFIDENTIAL

biopsy which is in excess of 10%, and after polling a number of clinicians who are involved in the diagnostic workup of patients with lung nodules, where this margin was considered reasonable.

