7.2 Reporting Period

The procedures being performed, bronchoscopy and CT-guided biopsy, are standard of care for management of indeterminate pulmonary nodules. Therefore, collection of data regarding adverse events and serious adverse events will be limited in this study:

- Any serious or non-serious adverse event related to research procedures (i.e. the consent process, HIPAA compliance, etc.) will be collected.
- After informed consent but prior to initiation of navigation bronchoscopy or CT-guided biopsy, serious and non-serious adverse events should be reported only if possibly, probably or definitely attributed by the patient's study physician to a protocol-mandated research procedure or intervention.
- The principal AE reporting period will be within 7 days of the study procedure, as it would be exceedingly uncommon for a new biopsy-related complication to occur more than 7 days after the biopsy procedure. Effort should be made on post-procedure day #7 to assess for any complications which have not already risen to investigator awareness.
- Any serious adverse event that occurs \leq 7 days after initiation of navigation bronchoscopy or CT-guided biopsy, regardless of causality to participation in the study, must be reported to the Coordinating Center in an expedited fashion as directed below (Reporting Procedures).

CONFIDENTIAL

During the 7-day reporting period, non-serious adverse events should only be recorded if, in the opinion of the investigator, there is a reasonable possibility the event is attributable to participation in the study. Non-serious adverse events related to navigation bronchoscopy or CT-guided biopsy or the next phase of the patient's treatment or management should NOT be recorded.

Participants should be instructed to report any serious post-study event(s) that might reasonably be related to participation in this study. The investigator should notify the IRB and the Coordinating Center of any unanticipated death or adverse event occurring after a participant has discontinued or terminated study participation that may reasonably be related to the study.

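### Complications of a further nodule biopsy after a non-diagnostic study biopsy are not clearly required to be collected or counted, although the margin is justified by pneumothorax

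*Combined protocol and SAP*

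**What the plan says.** **What follows a negative biopsy.** Section 4.9 lists three routes as examples: crossover to another minimally invasive biopsy, serial CT, or surgery. It then says: "These subsequent procedures will be part of normal patient care and only be regarded as follow-up data for the purpose of this study". The explanation attached to that sentence is about diagnostic yield only. Section 4.8 makes the need for an additional nodule biopsy a secondary endpoint, and Section 6.3 records the need for another biopsy modality.

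**What safety data are collected.** Section 7.2 says: "The principal AE reporting period will be within 7 days of the study procedure". It asks for serious events of any cause within those 7 days. It adds that non-serious events related to the two biopsies "or the next phase of the patient's treatment or management should NOT be recorded". Two other places have a wider reach. Section 7.7.2 requires all serious events to be reported, with no time limit in that statement. The assessment table in Section 16 marks adverse events at 3, 6 and 12 months.

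**What the endpoints cover.** Section 4.8 lists the rates of pneumothorax and of pneumothorax needing a chest tube. It does not say whether they count the assigned procedure or everything that follows.

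**Why this touches the margin.** Section 6.1 says: "The noninferiority margin has been chosen based on the known pneumothorax rate of CT" biopsy, put there at more than 10%, together with a poll of clinicians.

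**The concern.** The design accepts up to 10 points less accuracy in exchange for fewer complications. Lower accuracy has a safety cost of its own: a failed NB can lead to a CT-guided biopsy, the procedure with the higher pneumothorax rate. Inclusion criterion 2d requires every nodule to be reachable by both routes, so that fallback is feasible for each patient.

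Consider an NB patient with a non-diagnostic result who has a CT-guided biopsy at week 4 and then a pneumothorax. Under 7.2 the event lies outside the reporting window. Under Section 16 it might be picked up at the 3-month contact. Under 4.8 nothing says whether it counts towards the NB arm's rate. Sites could reasonably differ, and events not collected at the time may be hard to recover later. If only first-procedure rates are reported, the reader sees the safety gain from NB without the part that lower accuracy gives back.

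**Working it through.** **1. The plan's own figure.** The documents give no pathway-level complication rate. The related design figure is reproduced: n = (1.645 + 0.842)² × (2 × 0.90 × 0.10) / 0.10² = 111.3, so 112 per group; 112 × 1.15 = 128.8, so 129.

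**2. Inputs.**
- CT-guided biopsy (Section 3.1): "the rate of pneumothorax was 15% with need for chest tube management in 7" per cent.
- NB (Section 3.1): "bronchoscopic biopsy is safer with reported 1.6% pneumothorax, with a need for chest tube management in 0.7" per cent.
- NB accuracy: 90%, from the design assumption in Section 6.1 ("approximately 80% power if the true diagnostic accuracies are 90% for both arms"); 85%, from Section 3.1 ("the diagnostic yield approaches 85% in retrospective data"), which is a yield and not accuracy as the endpoint defines it; 80%, the 90% control assumption minus the 10-point margin.
- Share *x* of failed NB patients who go on to CT-guided biopsy: not given. Assumed values are 100%, 50% and 25%.

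**3. Formula.** With failure share *f* = 1 − accuracy, and independent risks,

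pathway rate = 1 − (1 − NB rate) × (1 − *f* × *x* × CT rate).

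Example, 80% accuracy and full crossover: 1 − 0.984 × (1 − 0.20 × 0.15) = 1 − 0.984 × 0.97 = 4.55%.

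**4. NB-pathway pneumothorax, with its ratio to 1.6%.**

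| NB accuracy | all cross over | half | a quarter |
|---|---|---|---|
| 90% | 3.08% (1.92) | 2.34% (1.46) | 1.97% (1.23) |
| 85% | 3.81% (2.38) | 2.71% (1.69) | 2.15% (1.35) |
| 80% | 4.55% (2.85) | 3.08% (1.92) | 2.34% (1.46) |

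Simple addition gives nearly the same: 1.6 + 0.20 × 15 = 4.6%, or 2.9 times.

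**5. NB-pathway chest tube, with its ratio to 0.7%.**

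| NB accuracy | all cross over | half | a quarter |
|---|---|---|---|
| 90% | 1.40% (1.99) | 1.05% (1.50) | 0.87% (1.25) |
| 85% | 1.74% (2.49) | 1.22% (1.74) | 0.96% (1.37) |
| 80% | 2.09% (2.99) | 1.40% (1.99) | 1.05% (1.50) |

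**6. Patients.** With full crossover among 129 NB patients, extra pneumothoraces are 129 × 0.10 × 0.15 = 1.9 to 129 × 0.20 × 0.15 = 3.9. Extra chest tubes are 129 × 0.10 × 0.07 = 0.9 to 129 × 0.20 × 0.07 = 1.8.

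**7. The CT arm.** If its 10% failures are all re-biopsied, pneumothorax becomes 1 − 0.85 × (1 − 0.10 × 0.016) = 15.14% when the second biopsy is NB, or 1 − 0.85 × (1 − 0.10 × 0.15) = 16.28% when it is CT-guided.

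**8. The contrast.** On first procedures alone the NB advantage is 15 − 1.6 = 13.4 points. At 80% NB accuracy with full crossover it is 15.14 − 4.55 = 10.6 points, or 16.28 − 4.55 = 11.7 points. The CT-to-NB ratio falls from 15 / 1.6 = 9.4 to 15.14 / 4.55 = 3.3, or 16.28 / 4.55 = 3.6.

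**The case against.** The other side has four good arguments.

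- **Section 4.9 does not exclude safety data.** A reader might infer from it that second-biopsy complications are barred from collection. The text does not say so. It keeps later procedures out of diagnostic yield, and follow-up data are themselves recorded under 6.3. This stands.
- **Section 7.2 cannot settle what the endpoints omit.** Read literally, it would also bar a non-serious pneumothorax from the assigned biopsy, which is a secondary endpoint. The endpoints must therefore draw on the complications variable in 6.3. This also stands, but that variable is listed among procedural characteristics and is not tied to any second biopsy. Nor do 7.7.2 and Section 16 cure the gap: a late event report would still reach the endpoints under no stated rule.
- **A per-procedure rate is a legitimate target.** The synopsis glosses the bronchoscopy pathway as navigation bronchoscopy, and 4.6 and 4.7 each describe one procedure. Such a rate is unbiased for what it measures. This stands; it is incomplete only when set against a margin that trades accuracy for safety.
- **The extra events are few, and NB keeps its advantage.** True on these figures. In absolute terms the CT arm can move almost as much: at 90% accuracy in both arms, repeat CT-guided biopsy adds 1.3 points to CT, against 1.5 points for NB with full crossover.

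**Conclusion.** The gap is one of undefined scope and conflicting sections. Collection of second-biopsy complications is neither clearly required nor clearly excluded, and 4.8 leaves the counting rule open.

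For NB accuracy of 90% to 80%, the NB-pathway pneumothorax rate would be about 1.9 to 2.9 times the first-procedure rate with full crossover, 1.5 to 1.9 times with half, and 1.2 to 1.5 times with a quarter. Chest-tube ratios are similar.

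Two stronger readings are tempting. The first is that the trial will understate NB harm two- to threefold. That needs nearly every failed NB to lead to CT-guided biopsy, whereas 4.9 also names serial CT and surgery, and it applies only to a pathway rate. The second is that the trial cannot judge its trade at all. The direction does not change (about 4.6% against 15.1–16.3% at the extreme), and the need for a further biopsy is reported. What changes is the size of the advantage.

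The figures assume that the patients without an accurate result are the ones re-biopsied, that the Section 3.1 rates apply to second biopsies, and that risks are independent. The crossover share is an assumption throughout.

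**What to change.** 1. Reconcile 7.2 with 7.7.2 and the Section 16 table, so that sites have one rule for events after day 7.
2. In 4.9, 7.2 and the case report form: for any further biopsy of the index nodule through 12 months, in both arms, record the modality and whether pneumothorax, chest tube placement, bleeding requiring intervention or hospitalization occurred within 7 days of it.
3. In 4.8: report each of these rates by randomized arm twice, once for the assigned procedure alone and once cumulatively for the pathway. Use the cumulative rate when safety is weighed against the accuracy margin.

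**Cost.** A short form block and one extra table. The synopsis already provides follow-up of up to one year after non-diagnostic or benign results. Sample size, decision thresholds and patient management are untouched. The downside is a little more data entry, and the need to obtain outside records for biopsies done elsewhere.
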